3.1.1.2 Part 2 (MAD)

The first cohort for Part 2 of this trial (Cohort 7) can begin after the FDA has reviewed and assessed the SAD safety and PK data and providing no halting criteria have been met. In Part 2, subjects in four cohorts of 8 subjects each (6 rezafungin, 2 placebo) will be randomized to receive SC doses of rezafungin or placebo on Days 1, 8, and 15 of the MAD portion of the study. Dose levels of rezafungin to be assessed will follow an ascending multiple-dose regimen (30 mg x 3 doses, 60 mg x 3 doses, 100 mg x 3 doses, and 200 mg x 3 doses). A schematic of the MAD study design is shown in (Table 2).

Table 2: Design for SC Dosing in MAD (Study Part 2)

Cohort	Dose (mg)	Dose Volume (mL)	Number of Doses	Number of Subjects*	
				Rezafungin SC Injection	Placebo
7	30	0.3	3	6	2
8	60	0.6	3	6	2
9	100	1	3	6	2
10	200	1 (in each of 2 injections)**	3	6	2
Total Number of Subjects				24	8
				32	

*Within each cohort two sentinel subjects will be admitted initially, and the randomization scheme will be designed to ensure that one subject will receive rezafungin and the other will receive placebo. All sentinel subject safety data through Day 30 will be reviewed by the PI prior to dosing the remainder of cohort. Safety data for each cohort through Day 30 will be confirmed by review of objective pre-defined criteria before continuing to the next cohort.

**The 200 mg (2 x 1 mL) SC dose will be injected as 1 mL each in the same abdominal quadrant, separated by approximately 5 cm. Each dose will be administered in a different quadrant (total 3 quadrants). Details are included in the MOP for this study.

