3.1.3 Dose Escalations

In Part 1/SAD, the initial cohort of 4 subjects will be administered 1 mg of rezafungin (3 subjects) or placebo (1 subject) as a single SC injection.

Dose escalation to each successive cohort during Part 1 will occur if none of the predefined dose escalation halting criteria are met through Day 30 (final visit). The FDA will review all safety and PK data from the SAD (Part 1) and determine if the study may proceed to the MAD (Part 2) and BA (Part 3) portions. Rezafungin doses for the MAD and BA portions will be determined after FDA review of the SAD data. Dose escalation during Part 2 will occur if none of the predefined dose escalation halting criteria are met through Day 30 after the first dose. This will be communicated through the following process:

1. An email from the site to the SDCC attesting that all data entry has been completed after the last subject has had their Day 30 visit, then data cleaning, as applicable, prior to the SDCC being able to generate the report.
2. A halting criteria report will be provided by the SDCC to DMID.
3. If based on the entered data in EDC, none of the escalation criterion is met, then the SDCC will open the database for the following cohort after confirmation from DMID that the study may proceed to the next cohort.
4. If any of the criterion is met, the SDCC will provide the dose escalation report and an ad-hoc SMC meeting will be convened to seek recommendation from the SMC.

Part 2 (MAD) and Part 3 (BA) may not begin until after FDA has reviewed all safety and PK data from Part 1 (SAD) and given agreement that it is safe to proceed. The doses for Parts 2 and 3 may be updated after FDA review of the SAD data. There will be a scheduled SMC data review meeting prior to start of Part 2 (MAD) Cohort 7.

In order to efficiently identify the optimal therapeutic doses for use in future clinical trials, a flexible scheme of dose escalation, (based on ongoing study data) will be used that allows intermediate doses higher or lower than the planned doses (30, 60, 100, and 200 mg), upon protocol amendment and with IRB approval. However, no cohort will be dosed higher than the 200 mg free base equivalent.

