Cohorts 2-6 in the SAD and all MAD cohorts will be conducted with sentinel dosing of rezafungin (i.e., dosing in 2 subjects followed by remaining six subjects). The randomization scheme will be designed to ensure that 1 subject will receive rezafungin and the other will receive placebo in sentinel dosing. The dosing of the remaining six subjects in the same cohort will not be initiated until a minimum of 4 weeks after the second sentinel dosing, and no serious adverse events (SAEs)/adverse events (AEs) have occurred that meet the predefined objective halting criteria for sentinels. The blinded safety and clinical laboratory data from all subjects in the cohort will be reviewed and confirm that none of the dose-escalation halting rules have been met before moving to the next higher dose cohort. If any of the predefined halting criteria is met, the study enrollment and dosing will be stopped until the SMC provides recommendations regarding continuation of the study (See [Section 8.2.3](#)).

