6.4.10 Day 30 (± 1 Day) – Follow-Up – Final Study Visit

- Obtain resting vital signs after being at rest for at least 5 minutes.
- 12-lead ECG after at least 5 minutes in the supine position (triplicate readings, at least 1 minute apart within a 15-minute period).
- Perform targeted PE.
- Obtain weight, calculate BMI.
- Obtain blood for hematology/coagulation/chemistry and urine for urinalysis.
- Perform serum pregnancy test (females of childbearing potential only).
- Obtain PK blood sample. No PK blood samples collected in Cohort 1.
- Assess reactogenicity at SC injection site(s) (see [Section 7.1.3](#) and MOP for this study).
- Assess AEs.
- Review Memory Aid.
- Review and record any concomitant medications and non-pharmacologic treatments/procedures since admission to the CRU.
- Review post-study instructions (contraceptive use, pregnancy reporting).

6.5 Part 2 (Cohorts 7 through 10)**6.5.1 Days 1, 8, and 15 – Inpatient CRU**

Study drug or placebo will be administered via SC injection in the morning on Days 1, 8, and 15. Subjects will be inpatients in the CRU and will undergo the following procedures, which are listed in the Schedule of Study Procedures and Evaluations ([Appendix A](#)) and detailed in Clinical Evaluations ([Section 7](#)):

- Randomize the subject (Day 1 only).
- Review inclusion criteria numbers 2-7 and 10-11, and exclusion criteria numbers 2-4 and 8-18 (from [Section 5.1.2](#)) to ensure the subject remains eligible for dosing (Days 8 and 15 only).
- Obtain resting vital signs before study drug dosing (within 60 minutes of study drug dosing for Day 1). This is to be documented as the Baseline prior to dosing on Day 1.
- Perform targeted PE.
- Obtain a 12-lead ECG before study drug dosing (Day 1 only) after at least 5 minutes in the supine position (triplicate readings, at least 1 minute apart within a 15-minute period) and within 60 minutes before study drug dosing.
- Baseline (Day 1) and pre-dose (Days 8 and 15) skin assessment at SC injection site area(s) prior to study drug dosing (see [Section 7.1.3](#) and MOP for this study).
- Administer study drug via SC injection in the abdomen at a slow, steady pace.
- Obtain vital signs at 15 minutes (± 5 min), 1 hour (± 10 min), and 2 hours (± 10 min) after dosing, after resting in a supine or semi-supine position for at least 5 minutes.

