6.5.8 Day 30 (± 1 Day) – Follow-Up - Outpatient

- Obtain resting vital signs after being at rest for at least 5 minutes.
- 12-lead ECG after at least 5 minutes in the supine position (triplicate readings, at least 1 minute apart within a 15-minute period).
- Perform targeted PE.
- Obtain PK blood sample.
- Assess reactogenicity at SC injection site(s) (see [Section 7.1.3](#) and MOP for this study).
- Assess AEs.
- Review Memory Aid.
- Review and record any concomitant medications and non-pharmacologic treatments/procedures since discharge from the CRU.
- Reminder of contraceptive use and post-discharge instructions (dietary and medication/nonmedication, vaccine and blood/blood product/sperm donation restrictions).

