8.7.2 Dose Escalation Halting Rules

Sentinel Subject Halting Rules

If any of the criterion below are met, the cohort will be suspended (enrollment and dosing), and the SMC ad hoc meeting will convene:

- Any SAE (regardless of the relationship to the study drug) through 48 hours post study drug administration.
- Any Grade 2 (or higher) adverse event deemed to be related to the study medication by the PI, having an initial onset within the first 72 hours post study drug administration that does not resolve within 72 hours from onset.
- Any subject experiences skin ulceration of any grade at an injection site.

Cohort Dose Escalation Halting Rules

If any of the criterion below are met, the escalation to the next cohort will be suspended (enrollment and dosing), and the SMC ad hoc meeting will convene.

- 2 or more subjects in a cohort experience the same grade 2 (or higher) related AE (laboratory or systemic) which is coded in the same HLTG per MedDRA coding, through Day 30 (SAD) or Day 30 (MAD) of the study.

- Two or more subjects within a cohort with post-dose QTcF > 500 or change from baseline >60 ms.
- Any subject experiences skin ulceration of any grade at an injection site.

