- i. A complete PE will be performed at Screening and targeted PEs will be performed on Days -1, 1, 2, 4, 7, 8, 9, 11, 14, 15, 16, 18, 21, 30 (± 1 day), and 45 (±1 day),
- j. ECGs will be obtained at Screening and on Day 1 within 30 minutes prior to study drug administration, and 4 hours (± 10 minutes) post-dose (Days 1, 8, and 15), Day 21, Day 30, Day 45, and Unscheduled visits
- k. Fasting (at least 8 hours) blood samples will be collected for hematology, coagulation and chemistries at Screening and on Days -1, 2, 9, 16, 7, 14, 21 and 45 (±1 day). Hematology tests consist of CBC with differential; coagulation tests consist of PT/PTT/INR; Chemistries panel includes albumin, glucose, blood urea nitrogen or urea, potassium, calcium, sodium, chloride,

total protein, creatinine, CO₂, CK, phosphorus, alkaline phosphatase, AST, ALT, total bilirubin, direct bilirubin,

- l. Urine will be collected for urinalysis, urine drug screen and urine alcohol at Screening, and on Day -1. Urine will be collected for urinalysis on Days 2, 7, 9, 14, 16, 21, and 45 (± 1 day),
- m. Blood for PK analysis (plasma) will be drawn pre-dose within 60 minutes before study drug dosing and at 0.5 h (± 5 min), 1 h (± 10 min), 2 h (± 10 min), 4 h (± 10 min), 6 h (± 10 min), 8 h (± 10 min), and 12 h (± 10 min), (Days 1 and 15); pre-dose within 15 minutes before study drug dosing and at 1 (± 10 min), and 4 hours (± 10 min), on Day 8; 24 hours (± 30 min), on Days 2 and 16; 48 hours (± 30 min) on Days 3 and 17; 96 hours (± 30 min, on Days 5, 12, and 19; and 144 hours (± 30 min) on Days 7, 14, and 21 after dosing; and on Days 30 (± 1 day) and 45 (± 1 day),
- n. Injection site assessment pre-dose and at 1 and 4 (± 10 min), 24, 48, 72, 96, 120, and 144 h (± 30 min) post-dose, Day 30 (± 1 day), and Day 45 (± 1 day). Unscheduled visits are not timed.
- o. Subjects are to be assessed for AEs occurring from the time of the first dose of study drug through Day 45 (± 1 day),
- p. Counsel/reminder on contraceptive use and post-discharge instructions (dietary and medication/nonmedication, vaccine and blood/blood product/sperm donation restrictions); as described in [Section 5.1](#).
- q. Memory Aid issued on Day 1, training on Day 7, and review on Days 30, 45 and at Unscheduled visits.

Table 13: Schedule of Study Procedures and Evaluations for Cohort 11 in BA (Part 3)

Procedures/Day	Screening	Baseline Check-in	Inpatient – Confined to CRU							FU	FU/ET	Unscheduled	

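### The Part 2 escalation rule counts laboratory AEs through Day 30, but no safety laboratory test is scheduled between Day 21 and Day 45

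*Protocol*

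**What the plan says.** The cohort rule in Protocol 8.7.2 applies to events of at least Grade 2, and its wording covers any "related AE (laboratory or systemic) which is coded in the same HLTG per MedDRA coding, through Day 30 (SAD) or Day 30 (MAD"). Sections 3.1.3 and 8.2.3 repeat the Day 30 cut-off. Under 3.1.3 the site confirms that data entry is complete "after the last subject has had their Day 30 visit", and the halting report is then prepared. Day 45 data are not awaited.

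For Part 2, Table 12 footnote k places hematology, "coagulation and chemistries at Screening and on Days -1, 2, 9, 16, 7, 14, 21 and 45". Footnote l says "Urine will be collected for urinalysis on Days 2, 7, 9, 14, 16, 21, and 45", after the Screening and Day -1 samples. The Day 30 visit in 6.5.8 lists vital signs, ECG, targeted examination, reactogenicity and AE assessment, and "Obtain PK blood sample", but no safety laboratory test. The Part 1 Day 30 visit (6.4.10) does include them: "Obtain blood for hematology/coagulation/chemistry and urine for urinalysis".

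Two sentinel provisions also apply. The Table 2 footnote says "All sentinel subject safety data through Day 30 will be reviewed by the PI prior to dosing the remainder of cohort". Section 3.1.3 says that dosing of the other six "will not be initiated until a minimum of 4 weeks after the second sentinel dosing".

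**The concern.** The rule names laboratory AEs and sets Day 30 as the end of counting, but the schedule gives it nothing to count after Day 21. The same wording works in Part 1, where Day 30 is a laboratory day. It does not work in Part 2, where Day 30 is no longer the final visit.

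This matters because laboratory abnormalities can be silent. Section 2.3.1 names abnormal liver function tests, hepatitis and hepatic failure as possible echinocandin class effects. Symptom review, vital signs and an ECG at Day 30 would not reveal a raised transaminase. A reader of the escalation report could take the absence of laboratory events on Days 22-30 as evidence of safety when no sample was scheduled.

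The PI's review of sentinel data through Day 30 has the same gap. The sentinel halting criteria for SAEs and for related Grade 2 or higher events do not, because their windows are 48 and 72 hours.

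**Working it through.** **1. Confirm the schedule against Table 9.** The laboratory days in footnote k are Screening, -1, 2, 7, 9, 14, 16, 21 and 45, which is 9 draws. Table 9 also shows 9 draws for each panel, and its totals reproduce:

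- Volume: 9×4 + 9×2 + 9×2.7 + 4 + 27×3 = 36 + 18 + 24.3 + 4 + 81 = 163.3 mL.
- Samples: 3×9 + 1 + 27 = 55.

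A Day 30 draw would make 10 per panel, so Table 9, the footnotes and the visit text agree that there is none. The Table 12 grid was not legible enough in the text available to me and is not used.

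**2. Size the gap.**

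- Days in the rule's window with no scheduled sample: 30 − 21 = 9 (Days 22-30).
- Interval between scheduled panels: 45 − 21 = 24 days.
- Last sample before the decision, relative to the last dose: 21 − 15 = 6 days in Part 2, against 30 − 1 = 29 days in Part 1.
- Decisions affected: three (cohorts 7 to 8, 8 to 9 and 9 to 10).

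**3. Who is exposed before the missing data arrive.** Take nominal days and no time at all for data entry or reporting. Sentinels start on calendar day 1, and the other six on day 31, after the sentinel Day 30 review. For those six (5 active, 1 placebo):

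| Event | Calendar day | Day on the six subjects' clock |
|---|---|---|
| Last scheduled panel before decision | 51 | 21 |
| Escalation decision | 60 | 30 |
| Next cohort's sentinels dosed | 61, 68, 75 | 31, 38, 45 |
| Next scheduled panel | 75 | 45 |
| Next cohort's other six, earliest | 89 to 91 | 59 to 61 |

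The range in the last row runs from the 4-week minimum (Day 31 + 28 = Day 59) to the day after the sentinels' Day 30 (Day 31 + 29 = Day 60, so Day 61). Only the next cohort's sentinel pair, one of them active, is therefore dosed ahead of the Day 45 samples. That subject receives two doses before the samples and the third on the same day. Over three escalations this is at most three active subjects. The current cohort's own sentinels reach Day 45 on calendar day 45, before the decision, but those results fall outside the rule's window.

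**4. Illustration of what the rule would miss.** Let p be the chance that an active subject has a related Grade 2 or higher abnormality, in the one MedDRA high-level group term, that first appears on Days 22-30 and is present at Day 30. The documents give no value for p, so these rates are assumptions. With 6 active subjects, P(2 or more) = 1 − (1−p)^6 − 6p(1−p)^5.

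| Assumed p | Rule met with a Day 30 panel | Rule met on scheduled samples as planned |
|---|---|---|
| 0.05 | 3.3% | 0% |
| 0.10 | 11.4% | 0% |
| 0.20 | 34.5% | 0% |
| 0.30 | 58.0% | 0% |

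The last column is zero by construction, because no scheduled sample exists to detect the event.

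**The case against.** The strongest reply is that 8.7.2 sets a cut-off for counting AEs and promises no particular sampling day. Part 2 keeps the Part 1 pattern: panels at 24 and 144 hours after each dose, and a final panel about a month after the last dose (Day 45 − Day 15 = 30 days, against 29 in Part 1). Part 1 itself has no scheduled panel on Days 8-29. All three doses are covered to 144 hours before the decision, so only onset 7 or more days after the last dose is missed. This is right as far as it goes, and it narrows the point to late onset. It does not explain a laboratory rule that runs to Day 30 without a sample there.

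Other safeguards exist:

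- Section 3.1.3 requires review of the cohort's clinical laboratory data before escalation.
- AEs are followed to resolution or stability.
- The PI or Medical Monitor can stop dosing at discretion (8.2.3).
- The study-wide five-subject rule in 8.7.1 runs throughout.
- FDA and the SMC review the single-dose data before Part 2.
- The current cohort's sentinel Day 45 results could inform discretion.

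None of these produces a Day 22-30 result for the other six subjects. Unscheduled visits (6.7) need a reason to call the subject back, and a silent abnormality gives none.

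The exposure figure is also a worst case. Data cleaning, the report and sponsor confirmation take time. If they took 15 days (an assumption), the next sentinels would start after the Day 45 samples, so the range is zero to three active subjects. The rates in the illustration have no support in the documents, and 2% would give only 0.6%. Both limits are accepted. Finally, no MAD subject was enrolled (SAP section 1), which limits the consequence but leaves the design gap.

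**Conclusion.** The concern holds. The Part 2 rule and the Part 2 schedule do not match: nine of the rule's thirty days have no scheduled laboratory sample, at each of three escalations. The conclusion rests on the visit text, footnotes k and l and the Table 9 count, which agree, and on no unscheduled sample being taken.

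The consequence is limited. Symptomatic events, vital signs and ECG changes are still captured at Day 30, early effects of the third dose are sampled on Days 16 and 21, and no more than three active sentinels could be dosed ahead of the Day 45 results. No subject or analysed result in this trial was affected. It should be corrected before any restart or reuse of the design.

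**What to change.** Add hematology, coagulation, chemistry and urinalysis to the Part 2 Day 30 visit, alongside the PK draw. Update 6.5.8, the Table 12 grid, footnotes k and l, and Table 9. The Day 30 wording in 8.7.2, 8.2.3 and 3.1.3 can then stand, and the sentinel review in the Table 2 footnote is covered as well.

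The cost is 4 + 2 + 2.7 = 8.7 mL of blood at an existing venepuncture, one urine sample, and an 8-hour fast that the visit does not now need, once for each of 32 subjects. Table 9 becomes 10 draws per panel, 58 samples and 163.3 + 8.7 = 172.0 mL on its own count. While editing it, reconcile the PK row: Table 6 implies 31 PK draws and Table 9 has 27. With 31, the total including the Day 30 panel is 172.0 + 4×3 = 184.0 mL.

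If the sponsor prefers not to add the sample, 8.7.2 and 3.1.3 should say that the laboratory part of the Part 2 rule rests on scheduled data through Day 21. That costs only wording but leaves the gap, so it is the weaker option.

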8.7.3 Individual Halting Rules

If any of the criterion below are met, the subject will be discontinued from further dosing:

- Any SAE regardless of the relationship to the study drug, throughout the duration of the study.
- Any other condition that the Site PI judges to unduly increase the risk to the subject.
- Any subject experiences skin ulceration of any grade at an injection site. (Does not apply to infusion site).

8.7.4 Infusion Halting Rules (Part 3 for IV Dosing Only)

Infusion of study drug will be halted if any of the following manifestations of anaphylaxis develop and will not be restarted:

- Skin or mucous membrane manifestations: hives, moderate or severe pruritus, flushing, swollen joints, swollen lips, tongue or uvula.
- Respiratory compromise: dyspnea, wheezing, stridor.
- A decrease in systolic blood pressure to <90 mmHg or $>30\%$ decrease from baseline blood pressure or a decrease in diastolic blood pressure of $>30\%$ from baseline.
- Tachycardia with an increase in resting heart rate to ≥ 130 beats per minute (bpm); or development of a ventricular dysrhythmia; or bradycardia <45 bpm (or <40 bpm in subjects with a baseline of <60 bpm) that is associated with complaints of dizziness, nausea, or feeling faint.
- Syncope.
- Confusion.

8.8 Safety Oversight (ISM and SMC)

8.8.1 Independent Safety Monitor

An ISM is a physician with relevant expertise whose primary responsibility is to provide to DMID an independent safety assessment in a timely fashion. This ISM is identified by the investigator site and approved by DMID. Participation is for the duration of the DMID study and is a voluntary position that does not receive payment. The ISM must meet the requirements of the NIAID conflict of interest policy.

The ISM:

- Is near the site and has the authority and ability to readily access subject records in real time.
- May be a member of the participating institution's staff but preferably be from a different organizational group within the institution.
- Should not be in a direct supervisory relationship with the PI.
- Should have no direct involvement in the conduct of this trial.

The ISM will:

- Sign a Conflict of Interest certification at the time they are asked to participate and provide updates to this information as needed.
- Receive reports of SAEs from the Site PI and will be notified by email when DMID is notified of the SAE.
- Evaluate the SAE and report their clinical assessment to DMID, through DMID-CROMS system organ classes (SOCS) in a timely manner using the attached report form and email the report to DMID-CROMS SOCS.
- Communicate with the Site PI as needed.
- Review additional safety related events at the request of DMID.
- Provide additional information to DMID by teleconference as requested.

8.8.2 Safety Monitoring Committee

This trial will utilize an SMC, an independent group of experts that advises DMID. The primary responsibility of the SMC is to monitor subject safety. The SMC is external to DMID and comprises at least 3 voting members. The SMC will consist of members with appropriate Phase 1 trial expertise to contribute to the interpretation of data from this trial. Its activities will be delineated in a SMC charter that will describe the membership, responsibilities, and the scope and frequency of data reviews. The SMC will operate on a conflict-free basis independently of the trial team. DMID or the SMC may convene ad hoc meetings of the SMC according to protocol criteria or if there are concerns that arise during this trial.

The SMC will review the safety data at the following timepoints:

- Organizational meeting (before starting this trial).
- Data review meeting, following completion of Part 1 and prior to Part 2 (MAD).
- Ad hoc meeting(s).
- Final review meeting, to be conducted 6-8 months after clinical database lock to review the cumulative unblinded safety data for this trial. Data will be provided in a standard summary format. The SMC may be asked to provide recommendations in response to questions posed by DMID.

All SMC reviews will be performed using unblinded data. Only blinded data will be presented during the open session. Study drug administration data, including dose interruptions, modifications, and the associated reason(s), will be reported to the SMC.

